### **8.12 Unanticipated Adverse Device Effect (UADE)**

An unanticipated adverse device effect means any serious adverse effect on health or safety or any life-threatening problem or death caused by, or associated with, a device, if that effect, problem, or death was not previously identified in nature, severity, or degree of incidence in the investigational plan or application (including a supplementary plan or application), or any other unanticipated serious problem associated with a device that relates to the rights, safety, or welfare of subjects. UADEs are to be recorded in the **Adverse Event CRF** and the event is to be submitted to the FDA as a supplement and to all reviewing IRBs and investigators within 10 business days after the sponsor first receives notice of the adverse event. The investigator is also required to adhere to the reviewing IRB requirements for reporting of any UADE.

### **8.13 Conversion to Open Surgical repair**

Conversion to open surgical repair may occur either at the initial implant procedure or subsequent to the initial procedure. Information regarding the surgical conversion will be recorded on the **Open Surgical Conversion CRF** and the **Adverse Event CRF**. In the event that a patient requires conversion from endovascular to open surgical repair, the explanted device should be sent to a pathologist for examination. Explant information will be recorded on the **Explant -CRF**. Surgical conversions will be reported in the progress report. The Follow-up visit schedule for surgically converted patients is at one month and one year post open conversion.

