Study Secondary Endpoints	
The following secondary safety endpoints will be evaluated at 30 days, 12 months and annually to 5 years after implantation of the B-TEVAR device:
 
 
• Mortality rates
 
• Aneurysm related mortality
 
• Major Adverse Events (MAE)
 
• Conversion to open repair
 
• Aneurysm rupture
 
 
The following secondary effectiveness endpoints will be evaluated at 30 days, 12 months and annually to 5 years after implantation of the B-TEVAR device:
 
 
• Technical Success
 
• Freedom from Type I & III endoleaks
 
• Freedom from stent graft migration
 
• Freedom from aortic aneurysm enlargement
 
• Freedom from aneurysm rupture
 

	
 
• Freedom from conversion to open repair
 
• Radiographic evidence of device integrity
 
• Freedom from thromboembolic events
 
• Freedom from re-intervention
 

Clinical Utility Measurements	
The following Clinical Utility Measurements will be evaluated:
 
 
• Conduit usage
 
• Blood loss
 
• ICU stay
 
• Length of hospital stay
 
• Type of anesthesia
 
• Secondary interventions
 

Patient Population	
The total Treatment Group includes 60 patients, including those who are planning to undergo single or two-staged approach to repair.

Follow-Up Intervals	
Treatment Group follow up intervals will consist of 1, 6, and 12 months following the B-TEVAR implant procedure, then annually through 5 years.

Follow- Up Events	
Treatment Group follow up:
 
 
• Physical exam
 
• Contrast Enhanced Spiral Chest/Abdominal/Pelvic CT
 
• Device/aneurysm assessment based on imaging
 
• Laboratory Assessment
 
• Assessment of Adverse Events
 
• Assessment of concomitant medications (only anticoagulants, anti-platelets, antibiotics, statins, Beta blockers and ACE inhibitors/ARB)
 

Investigational Sites	
The University of Washington (University of Washington Medical Center and Harborview Medical Center) will be the only site involved in this trial.

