Patients will be enrolled in B-TEVAR study with a plan for 2 different pathways to treatment, either in single sitting or in a staged approach. For those patients in whom a staged approach is planned or considered, consent will be obtained and the patient enrolled prior to undergoing the TEVAR 1st stage of the procedure. These patients will be tracked with a separate follow up case report form at 1 and 12 months and annually to 5 years or until they undergo the second stage with a branched device, at which time their outcomes will be followed according to the routine case report forms. Some patients who undergo the 1st stage will not go on to have the second stage done with a branched graft. This could be due to the determination that they can indeed tolerate open repair, or due to a complex recovery after the 1st stage TEVAR. Such patients will be followed up to 5 years after enrollment. All patients who are enrolled will be followed and reported on. Patients who undergo the first stage, but not the second stage, will be reported as a sub-group of patients in the annual report.

All patients who undergo the first stage TEVAR will be treated with the same TX2 device that is in the B-TEVAR protocol. The specific peri-visceral device used for the second stage could be any one of the 5 device options, CMD, t-Branch, LP CMD or t-Branch or physician modified.

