### 8.6 Surgical Conversion

Surgical conversion occurs when a patient implanted with a physician modified endovascular graft undergoes open surgical repair with explantation of the stent graft. The follow-up for patients who are converted to open surgical repair include collection of the following data: Physical Exam and assessment of Adverse Events. The visits are to occur at 1 month post open conversion and 1 year post open conversion.

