### **8.11 Major Adverse Events (MAE)**

The following specific events will be considered major adverse events (MAE) for the purpose of evaluating the primary (30 day) and secondary (1 year) safety endpoints:

- Death
- Paralysis (excludes paraparesis)
- Myocardial Infarction
- Stroke (excludes TIA)
- Renal Failure (excludes renal insufficiency)
- Respiratory Failure (excludes COPD or pulmonary complications)
- Bowel Ischemia
- Lower Extremity Ischemia
- Procedural Blood Loss ( $\geq 1,000$  cc)

A MAE may or may not be considered related to the device. Mortality will be reported as “all cause” and “TAAA related.” All deaths occurring in the first 30 days post-index procedure are considered “TAAA related.”

The Clinical Events Committee (CEC) shall determine which adverse events in addition to those listed above in Section 8.11 are considered Major Adverse Events for evaluation of the primary (30 days) and secondary (1 year) safety endpoints.

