## 9.2 Secondary Endpoints

### 9.2.1 Safety

The following secondary safety endpoints will be evaluated at 30 days, 12 months and annually to 5 years:

- All-cause mortality
- TAAA Related Mortality
- Freedom from permanent spinal cord injury
- Major Adverse Events (MAE)
- TAAA rupture
- Surgical conversion

The CEC will meet annually to review all MAE. All deaths that occur in the study will be adjudicated by the CEC. TAAA related death is any death determined by the CEC to occur as a result of the initial procedure (first 30 days or prior to hospital discharge), TAAA rupture, conversion to open surgical repair, or due to secondary intervention after B-TEVAR.

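### Subjects converted to open repair have no scheduled contact beyond 1 year after conversion, although secondary mortality endpoints run to 5 years from implantation

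*Protocol*

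**What the plan says.** Two sections set the schedule after open conversion, and they agree. Section 8.13: "Follow-up visit schedule for surgically converted patients is at one month and one year post open conversion". Section 8.6: "The visits are to occur at 1 month post open conversion and 1 year post open conversion". Section 8.6 also fixes the content: "The follow-up for patients who are converted to open surgical repair include collection of the following data: Physical Exam and assessment of Adverse Events". Nothing in the protocol schedules a later visit, telephone call or vital-status check for these subjects.

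The secondary safety endpoints run longer. Section 9.2.1: "The following secondary safety endpoints will be evaluated at 30 days, 12 months and annually to 5 years". Its list includes all-cause mortality, TAAA-related mortality, MAE, rupture and surgical conversion. The Protocol Summary gives the same times and anchors them to implantation: "The following secondary safety endpoints will be evaluated at 30 days, 12 months and annually to 5 years after implantation of the B-TEVAR device". Section 8.11 has a shorter horizon for MAE, defining the events for the purpose of "evaluating the primary (30 day) and secondary (1 year) safety endpoints".

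On who stays under follow-up, section 2.1.4 says in general terms "All patients who are enrolled will be followed and reported on". Of subjects who have the first-stage TEVAR but no branched second stage, it says "Such patients will be followed up to 5 years after enrollment". Section 5.3 does not list conversion among the reasons for withdrawal. Section 6.5 says that all subjects who receive the B-TEVAR device are followed on the B-TEVAR Follow-up CRF and analysed as one group, with time counted from implantation.

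**The concern.** A converted subject remains in the study, since conversion is not a withdrawal reason, and belongs to the group whose mortality is to be evaluated yearly to 5 years. Yet the specific rule in 8.6 and 8.13 schedules nothing for that subject beyond 1 year after conversion. A subject who never received a branched device is followed to 5 years; one whose branched device had to be removed is not.

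The gap does not fall at random. Conversion is itself a failure component of the primary effectiveness composite in section 9.1.2, so follow-up thins out because the device failed. If later survival differs between converted and other subjects, the year 2 to 5 secondary safety estimates rest on incomplete data from the subjects in whom the device did worst. No analysis plan can recover a vital status that was not collected.

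**Working it through.** The protocol gives no figure to reproduce here, so the check is schedule arithmetic and a bound.

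**Inputs.** Last scheduled visit 12 months after conversion (8.6, 8.13). Safety horizon 60 months from implantation (9.2.1, Protocol Summary). Annual visits at years 2 to 5, each with a window of 60 days either side (6.5). Enrolment of 60 (5.0). Conversion rate: not stated.

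**Step 1: unscheduled time.** For conversion at month t after implantation, gap = max(0, 60 − (t + 12)) months.

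| Conversion at | Last scheduled visit | Gap (months) | Annual time points not covered |
|---|---|---|---|
| Implant | Month 12 | 60 − 12 = 48 | Years 2, 3, 4, 5 |
| Month 6 | Month 18 | 60 − 18 = 42 | Years 2, 3, 4, 5 |
| Year 1 | Month 24 | 60 − 24 = 36 | Years 3, 4, 5 |
| Year 2 | Month 36 | 60 − 36 = 24 | Years 4, 5 |
| Year 3 | Month 48 | 60 − 48 = 12 | Year 5 |
| Year 4 or later | Month 60 or later | 0 | None |

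The gap is therefore confined to conversions before about year 4, and it shrinks as conversion comes later.

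**Step 2: effect on a 5-year proportion.** A converted subject of unknown later status may be alive or dead at year 5. With 60 in the denominator, k such subjects widen the worst-case range by k/60: 1/60 = 1.7 points, 2/60 = 3.3, 3/60 = 5.0. Section 6.5 analyses first-stage-only subjects separately, so the weight per subject rises if the B-TEVAR denominator falls below 60.

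**Step 3: the same bound under Kaplan-Meier censoring.** If converted subjects were censored at their last visit (an assumption), their weight would pass to those still at risk. If all k then died before year 5, mortality would be understated by (k/60) × s, where s is the others' conditional survival from the censoring time to year 5. With s from 0.5 to 0.8 (assumption), one subject gives 1.7 × 0.5 to 1.7 × 0.8, about 0.8 to 1.3 points; three give 5.0 × 0.5 to 5.0 × 0.8 = 2.5 to 4.0 points. If converted subjects who reach their 1-year visit then survive as well as the others, the bias is zero; if they survive better, it reverses.

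**Step 4: how likely the situation is.** The chance of at least one conversion among 60 is 1 − (1 − p)^60. At assumed rates p of 1%, 3% and 5% it is 45%, 84% and 95%. The chance of three or more (binomial) is 2%, 27% and 58%. These count conversions at any time; only those before about year 4 open a gap.

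**Step 5: primary endpoints.** For the 30-day MAE endpoint, conversion at implant still has a 1-month visit. For the 12-month effectiveness composite, conversion within the period is a failure whatever happens later. Neither depends on contact after the 1-year post-conversion visit.

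**The case against.** The strongest reply is that 8.6 and 8.13 set a visit schedule and nothing more. A reader might infer that converted subjects leave the study, that their later deaths cannot be observed, or that they are censored so that 2- to 5-year mortality looks better than it is. The documents support none of these. No section says converted subjects exit. Section 8.15 requires annual reporting of deaths that are not device related, with no exception for converted subjects, and section 9.2.1 has the CEC adjudicate all deaths in the study. A late death that becomes known is therefore still reportable. The protocol states no censoring rule; that belongs in an analysis plan, which is not at hand.

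Further points stand. The conversion itself is well captured: it counts in the primary composite and as a secondary safety endpoint, and has its own CRF. The visits at 1 month and 1 year plausibly cover the period when deaths caused by conversion are most likely. Under section 8.15, a death after a secondary procedure counts as aneurysm-related only within 30 days, rupture apart, although section 9.2.1 sets no time limit for deaths resulting from conversion. The sentence in 2.1.4 about following all enrolled patients gives no duration and sits in a paragraph on staged repair, so it does not by itself contradict a two-visit schedule. The 5-year MAE horizon is weakened by section 8.11.

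What the reply does not remove is the mismatch for all-cause mortality, which depends on neither 8.11 nor the choice of definition. Passive reporting is not a scheduled check, and the general wording in 6.5 does not clearly override a specific rule stated twice. A reduced schedule after removal of the device may be sensible for imaging, but that does not account for the absence of a vital-status check.

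**Conclusion.** The point holds as a gap in scheduled data collection. For conversions before about year 4, sections 8.6 and 8.13 schedule no active contact for up to 48 of the 60 months over which section 9.2.1 evaluates mortality. Because conversion triggers the gap, it may be informative for the year 2 to 5 secondary safety estimates. The effect is at most 1.7 points on a 5-year proportion per converted subject of unknown status, taking 60 as the denominator, and less under Kaplan-Meier censoring. The number of conversions is unknown, and so is the direction of any bias.

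It does not establish that 5-year mortality will be understated, and the primary endpoints are essentially untouched. In a 60-patient single-arm feasibility study this is a modest but selective weakness that is cheap to close.

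**What to change.** Reconcile 8.6 and 8.13 with 9.2.1. Keep the two post-conversion visits and add one sentence to each section providing annual vital-status and adverse-event contact, by telephone or record review, to 5 years from the B-TEVAR date, so that converted subjects stay in the mortality estimates. At the same time, align the secondary MAE horizon in 8.11 with that in 9.2.1 and the Protocol Summary. No additional imaging is needed for this purpose.

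The cost is a few telephone or chart checks per converted subject: at most four annual contacts, for a conversion in the first year.

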### **8.14 Technical Failures**

In the event that a branched stent graft could not be deployed due to a technical failure, device failure information will be captured on the **Device Failure CRF**.

### **8.15 Deaths**

Any deaths that are device related must be reported to the FDA via an IDE supplement within 10 business days of knowledge of the event. Any deaths that are not device related are reported annually. The investigator is also required to adhere to the reviewing IRB requirements for reporting of deaths. In addition, patients with an implanted device who expire before completing the study should have the device explanted for evaluation by a pathologist if possible.

Aneurysm related death is defined as:

- any death occurring within 30 days of the B-TEVAR procedure, regardless of cause,
- death due to aneurysm rupture or
- within 30 days following any secondary procedure intended to treat the aneurysm.

## 8.16 Explants

Specific instructions for managing the removal and handling of the explanted device can be found in **Appendix VII: Explant Procedure** and Manual of Operations. Explant information will be recorded on the **Explant CRF**.

## 9.0 ENDPOINTS AND TECHNIQUES FOR MEASUREMENT

**The same endpoints will be measured for all different graft constructs. They will be reported as both a pooled group as well as separately by aortic endograft construct (physician modified, CMD, and t-Branch.)**

### 9.1 Primary Endpoints

#### 9.1.1 Safety

The primary safety endpoint is the rate of major adverse events (MAE) at 30 days post branched TEVAR repair. The following specific events will be considered major adverse events: MAEs are defined as any one of the following events:

- Death
- Paralysis (excludes paraparesis)
- Myocardial Infarction
- Stroke (excludes TIA)
- Renal Failure (excludes renal insufficiency)
- Respiratory Failure (excludes COPD or pulmonary complications)
- Bowel Ischemia
- Lower Extremity Ischemia
- Procedural Blood Loss ( $\geq 1,000$  cc)

MAEs may or may not be considered related to the device. Mortality will be reported as “all cause” and “TAAA related.” All deaths occurring in the first 30 days post-index procedure are considered “TAAA related.”

#### 9.1.2 Effectiveness

The primary effectiveness endpoint is the proportion of treatment group subjects that achieve treatment success with the B- TEVAR procedure, whether via the staged approach or done as a single procedure . Treatment success is a composite endpoint assessed at 12 months after the B-TEVAR procedure is performed that requires all of the following criteria to be met in order for a patient to be considered a treatment success:

- Technical Success, defined as successful delivery and deployment of the endovascular graft with preservation of unimpeded flow to those branch vessels intended to be preserved.
- Freedom from Type I & III endoleak. Type I and III endoleaks will be assessed by the investigator using Spiral CT images.
- Freedom from stent graft migration. Migration of the aortic stent graft is defined as evidence of proximal or distal movement of the stent graft >10 mm relative to fixed anatomic landmarks. Migration of a branch is defined as movement of the stent in relation to fixed anatomic location that results in a Type I or III endoleak. Spiral CT images will be used by the investigator to determine migration from the one month (baseline) CT image.
- Freedom from TAAA enlargement. Sac enlargement is an increase in aneurysm diameter (>5 mm) from the one month (baseline) post-operative measurement will be considered TAAA enlargement, as determined by the investigator.
- Freedom from TAAA rupture
- Freedom from conversion to open repair

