#### **7.1 Primary Objectives**

The primary objective of this study is to determine if branched endovascular grafts are a safe and effective method of treating TAAAs. Treatment success is defined as successful deployment of the modified endograft and its branches with preservation of unimpeded flow to all target vessels that are intended to be preserved. Failure to exclude the aneurysm (i.e. Type 1 or 3 endoleak), conversion to an open operation, aneurysm rupture, thrombo-embolic complication to a target

vessel, kink/stenosis of a branch stent or flow limiting distal branch vessel dissection will be considered treatment failure. Any such branch related events that are identified intra-operatively and successfully treated will not be considered treatment failures.

The safety of the endovascular grafts will be determined by the proportion of patients with major adverse events. The effectiveness of the endovascular grafts will be determined by the proportion of patients that achieve treatment success.

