### **8.3 Patency/ Branch Vessel Patency**

Patency is defined as the preservation of unimpeded flow to the treated vessel. Thrombo-embolic complication to a target vessel, kink/stenosis of a branch stent or flow limiting distal branch vessel dissection will be considered loss of branch patency. This may be evidenced by: CT, angiography, ultrasound or other imaging modality, or pathological analysis. Flow limiting findings on screening CT scans or by elevated Creatinine will be evaluated with further confirmatory studies, including clinical examination, duplex, and angiography as indicated.

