### 1.2.2 Secondary Effectiveness

The following secondary effectiveness endpoints will be evaluated at 30 days, 12 months and annually to 5 years:

- Need for re-intervention

- Treatment success as defined in section 9.1.2

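### Treatment success, the primary effectiveness endpoint, is defined by two lists that do not match (section 7.1 against 9.1.2 and the Summary), and 9.1.2 leaves open whether and when later branch loss counts

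*Protocol*

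**What the plan says.** Section 9.1.2 is the primary effectiveness endpoint: "Treatment success is a composite endpoint assessed at 12 months after the B-TEVAR procedure is performed that requires all of the following criteria". The six criteria are Technical Success and freedom from Type I and III endoleak, stent graft migration, aneurysm enlargement, rupture and conversion to open repair. Branch flow appears only within Technical Success, worded as "successful delivery and deployment of the endovascular graft with preservation of unimpeded flow to those branch vessels intended to be preserved". The Protocol Summary lists the same six items at 12 months.

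Section 7.1 also defines treatment success. It starts from successful deployment with flow kept to all intended vessels. It then names as failures Type 1 or 3 endoleak, conversion, rupture, thrombo-embolic complication to a target vessel, and two further branch events: "kink/stenosis of a branch stent or flow limiting distal branch vessel dissection will be considered treatment failure". It adds an exemption: "Any such branch related events that are identified intra-operatively and successfully treated will not be considered treatment failures". It gives no assessment time and mentions neither migration nor enlargement.

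Three other places bear on the reading:

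- Section 8.3: "Patency is defined as the preservation of unimpeded flow to the treated vessel". It then says that "kink/stenosis of a branch stent or flow limiting distal branch vessel dissection will be considered loss of branch patency", with thrombo-embolic complication treated the same way.
- The Summary's secondary effectiveness list schedules Technical Success for evaluation at 30 days, 12 months and annually to 5 years.
- The secondary effectiveness list in section 9 (numbered 1.2.2) includes "Treatment success as defined in section 9.1.2".

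**The concern.** Section 7.1 closes by saying that the proportion achieving treatment success determines effectiveness, and 9.1.2 makes that proportion the primary effectiveness endpoint. If the term has two meanings, the same subject can be counted differently depending on which section is applied.

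Choosing 9.1.2 does not fully settle the matter. The study's stated goal in section 1.0 includes preserving the visceral vessels. Whether a branch that is open at the end of the operation and lost later makes the subject a failure is therefore central to what the primary rate means. The imaging items are also judged at the site: for example, "Type I and III endoleaks will be assessed by the investigator using Spiral CT images". A rule left open is then settled case by case by people who know the outcome.

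**Working it through.** The protocol derives no sample size or power from this endpoint, so there is no figure to reproduce. The check sets the definitions side by side and then does simple arithmetic on reclassified subjects.

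**Item by item**

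| Element | 7.1 | 9.1.2 and Summary |
|---|---|---|
| Deployment with flow to intended vessels | yes | yes (Technical Success) |
| Type I/III endoleak, rupture, conversion | failure | failure |
| Target-vessel thrombo-embolism, branch kink/stenosis, flow-limiting dissection | failure | not named |
| Exemption for branch events fixed during the operation | yes | not stated |
| Aortic migration over 10 mm | not listed | failure |
| Enlargement over 5 mm | not listed | failure |
| Assessment time | none | 12 months |

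Section 7.1 does mention failure to exclude the aneurysm, but it spells that out as Type 1 or 3 endoleak, so sac growth without such a leak does not fall under it. Branch migration is not a separate difference: 9.1.2 defines it by a resulting Type I or III endoleak, which also fails 7.1.

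**Three test subjects**

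1. Sac growth of more than 5 mm by month 12, patent branches, no Type I/III leak: fails 9.1.2, has no listed failure under 7.1.
2. Branch stenosis at month 6, still present at month 12, no leak: fails 7.1. Passes 9.1.2 if Technical Success is procedural only. Fails it if the flow criterion is read with 8.3.
3. Branch stenosis at month 6, re-treated and patent at month 12: fails 7.1, whose exemption covers only intra-operative treatment. Even read with 8.3, this subject can pass a composite judged by status at 12 months, and fails only if loss at any time up to that visit counts.

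**Effect on the rate**

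Let n be the denominator, b the subjects failing only under 7.1 and g those failing only under 9.1.2. Then

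rate(9.1.2) − rate(7.1) = (b − g)/n.

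The protocol gives no value for b or g. Subject 1 adds to g. Subjects 2 and 3 can add to b. Because 7.1 has no time limit, an event after month 12 could also add to b. The sign is therefore open whichever way 9.1.2 is read.

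One subject is worth:

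- 1/60 = 1.7 percentage points if all 60 enrolled subjects are in the denominator;
- 1/50 = 2.0 or 1/40 = 2.5 points if 10 or 20 of the 60 never receive B-TEVAR. The 10 and 20 are assumptions. The Summary counts planned two-stage patients among the 60, and section 6.5 analyses separately those who do not reach the second stage.

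Purely as illustration, a net difference of three subjects is 3/60 = 5.0, 3/50 = 6.0 or 3/40 = 7.5 points.

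Two assumed cases at n = 60 show that the sign can go either way. In both, 48 of 60 subjects (80.0%) meet the shared items.

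- Six fail on branch events only and none on migration or enlargement: 7.1 gives 42/60 = 70.0%, and 9.1.2 with procedural Technical Success gives 48/60 = 80.0%.
- None fail on branch events and three fail on migration or enlargement only: 7.1 gives 48/60 = 80.0%, and 9.1.2 gives 45/60 = 75.0%.

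**The case against.** The strongest reply is that the governing text can be identified. Section 9.0 is the endpoint section. Section 9.1.2 names the primary effectiveness endpoint, fixes the time and requires every criterion. The Summary repeats its six items, and the secondary list cites it. Section 7.1 sits under objectives, and no other section cites it. This stands: a reader might infer that the sponsor has no stated endpoint or may choose between two, and the documents do not support that. It does not remove the conflict, because 7.1 says it is defining the term, lists failures and adds a classification rule found nowhere in 9.1.2. The one cross-reference concerns the secondary endpoint only.

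A second reply is that 7.1 does not call its failure list exhaustive. That is fair, so the claim for subject 1 is only that 7.1 lists no failure for that case.

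A third reply is that the protocol leans towards counting branch loss: 8.3 uses the same flow wording and names the same three events, and the Summary evaluates Technical Success repeatedly after the procedure. This also stands. A reader might infer that 9.1.2 ignores late branch loss, and that is too strong. But 9.1.2 does not refer to 8.3, and neither place says how a branch lost and then restored is counted.

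Finally, this is a single-arm feasibility study, the components are largely reported separately, and either rate could be rebuilt from planned data. That limits the consequence and makes the repair easy. An SAP, not at hand, might choose one reading, but the protocol would still contain both definitions.

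**Conclusion.** The protocol is wrong as written on this point: it is internally inconsistent about its primary effectiveness endpoint. The two lists differ in both directions and in timing. Section 9.1.2 is the likely governing text, yet it does not settle whether later branch loss counts, or whether loss repaired before month 12 does.

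The size is 1.7 percentage points per reclassified subject at n = 60, or 2.0 to 2.5 points under the assumed denominators of 50 and 40. It is larger again in the results by graft construct that section 9.0 also requires. How many subjects would be reclassified is unknown.

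Two stronger inferences are not supported. One is that reading 9.1.2 with 8.3 must give a rate equal to or below that under 7.1; subject 3 shows why it need not when status is judged at 12 months. The other is that a test could change its result; the protocol states no performance goal, so only the reported rate and its meaning are affected. The mismatch itself rests on the text alone. This should be fixed, but it does not invalidate the study.

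**What to change.** Make 9.1.2 the single definition. Replace the list in 7.1 with a reference to 9.1.2, and have the Summary refer there as well. This also removes the Summary's narrower wording of Technical Success, which mentions only the physician modified graft.

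In the flow criterion of 9.1.2, refer to branch patency as defined in 8.3, carry over the intra-operative exemption from 7.1, and state which of two rules applies:

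- patency as status at the 12-month visit; or
- freedom from loss of patency through the 12-month visit.

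This is a substantive choice and should be presented as one. The second rule counts branch losses repaired before month 12 as failures. It agrees with 7.1, where only intra-operative treatment is exempt, and compared with the first rule it can only lower the rate or leave it unchanged.

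Section 2.1.4 shows that the study is already screening and enrolling, so date the change and also report the rate under the alternative reading. That guards against a choice made with results in view.

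The cost is small. Patency is already assessed at each B-TEVAR follow-up visit (section 6.5 and Appendix IV), so no new data are needed. The change requires the prior IRB and FDA approval set out in section 11.8. The remaining drawbacks are a mid-study clarification and a possibly lower headline rate.
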